**For Protocol Office use only:**

Protocol title: The Effects of Hyperbaric Oxygen on  
Rheumatoid Arthritis: a Pilot Study.  
FDG20160004H wAMD13

investigator name redacted 28 Jan 20

DGMC Human Research Protocol Template

from wrists to proximal phalanges. BMP is done pre-MRI to guarantee adequate kidney function.

- Subjective patient reporting will be captured using the RAPID 3.
  - Sleep quality will be tracked using the Pain and Sleep Quality Questionnaire (PSQ-3).
  - Visual Analog Score for Pain (VAS) will be tracked.
  - Surveys will be administered by a study team member.
5. The subject at this time will be scheduled to start HBO2 treatments. Screening, baseline , first HBO2 treatment all in one month.
6. **During the period that the HBO2 treatments** are taking place the hyperbaric physicians will continue to monitor the subjects and if there is any concern regarding their physical condition they will consult with one of the rheumatologists. Participants will complete 30 sessions within 10 weeks.
7. If the subject reports pain relief, as defined as improvement of pain of > 40% or zero pain, during the HBO2 treatments they will be referred to the rheumatologist for assessment. Pain improvement will be based on a pain assessment (numerical pain scale of 1-10 reported verbally) at hyperbaric treatment visits. Labs (CPR, ESR and Microparticles) will be drawn at this time. RAPID 3 and PSQ-3 and VAS will be done at least six times while undergoing hyperbaric treatments to track subject progress. Labs (CRP, ESR and Microparticles) will be repeated at the conclusion of the HBO2 treatments.
8. At the **month three visit** (+/- 2 window) the subject will see the rheumatologist to track disease activity using the DAS-28. The date of the three month visit will be scheduled for three months from the Baseline visit. The Rheumatologist will order the MRI Ultrasound, and lab studies prior to the three month visit. RAPID 3, PSQ-3 and VAS for pain will be administered at this time. Laboratory samples will be collected prior to the Rheumatology appointment.
9. At the **month six visit** (+/- 2 week window) the subject will see the rheumatologist to track disease activity using the DAS-28. The date of the six month visit will be scheduled for six months from the baseline visit. The Rheumatologist will order the MRI, Ultrasound, and lab studies prior to the six month visit. RAPID 3, PSQ-3 and VAS for pain will be administered at this time. Laboratory samples will be collected prior to the Rheumatology appointment.

This marks the end of the trial. Patients will continue to be followed in the Rheumatology Clinic every three months.

**Study Visits**

	Screening Visit (maybe split into 2 visits) ***	Base line Visit ***	HBO TX ***	Pain relief during HBOT	Compl etion of HBOT	Mo 3 (+/- 2 weeks)	Mo 6 (+/- 2 weeks)
--	--	--	---------------------------	--	------------------------------------	-----------------------------------	-----------------------------------

ICD/ HIPAA	X						
Inclusion/ Exclusion Criteria	X						
Exam by Hyperbaric Physician	X						
Trial HBOT	X						
Hyperbaric treatments			X 30 * **				
Rheumatology Visit		X		X		X	X
Labs		X		X	X	X	X
Ultrasound		X				X	X
MRI		X				X	X
DAS 28		X		X		X	X
RAPID 3		X	X ****	X		X	X
PSQ 3		X	X ****	X		X	X
VAS Pain		X	X *****	X		X	X

\*When subject reports pain relief during HBOT they will be assessed by Rheumatologist.

\*\* Complete 30 HBO treatments within 10 weeks.

\*\*\* Screening, Baseline, First HBOT treatment all within one month (four weeks)

\*\*\*\* at least 6 times while undergoing hyperbaric treatments

The optimal dose response of RA patients to HBO2 is unknown. Modest benefit has been shown in prior studies at 2 ATA and 1.5 bar for 10 and 9-11 sessions, respectively. The subject will be compressed with air in the hyperbaric chamber to 2.0 ATA, and then placed on 100% oxygen by a head tent or mask, for 90 minutes. After hood removal, the chamber is decompressed while the patient breathes chamber air. Treatments are daily, Monday through Friday for a planned total of 30 sessions. Time to change in subjective study outcomes (relief of joint pain, stiffness, improvement in sleep patterns, and increase in activity level) will be documented. Treatments will stop at the end of 30 sessions whether or not there is subjective improvement. After the initial assessment, follow-up with the rheumatologist is scheduled at three and six months which is standard of care for rheumatology patients. If the participant

**For Protocol Office use only:**

Protocol title: The Effects of Hyperbaric Oxygen on  
Rheumatoid Arthritis: a Pilot Study.  
FDG20160004H wAMD13

investigator name redacted 28 Jan 20

DGMC Human Research Protocol Template

experiences subjective improvement during the 30 hyperbaric sessions, he/she will be assessed by one of the rheumatologists at the time of improvement. The hyperbaric physicians will be monitoring the patients daily, five days/week, and provide ongoing clinical assessments during the hyperbaric treatments. This is standard of care for HBO2 patients.

If the patient's RA symptoms worsen during the study, the plans are to:

1. Schedule an appointment with the the Hyperbaric and Rheumatology physicians to clinically evaluate and determine the cause. If it is determined that the symptoms could be due to HBO2, the treatment will be stopped and the Research Monitor will be notified.
2. The physicians will institute measures to address the cause.
3. If cause cannot be diagnosed and symptoms persist despite appropriate measures and if believed the patient may worsen from continued HBO2, treatments will be suspended.
4. Any adverse events will be recorded and reported to the IRB according to the AFI 40-402 and SGSE Operating Instructions and the Medical Monitor will be notified (see Section 6.7)

### **6.5. Risks/Benefits:**

All diagnostic and therapeutic procedures associated with subject qualification for, or participation in this study will be documented in standard patient record format. Copies of documentation will be placed in both the patient's medical record and the associated patient study record.

### **Risks/ Inconveniences:**

**Middle ear barotrauma and eustachian tube dysfunction** is the most common side effect of HBOT with an incidence of at least 2%. Sinus barotrauma is even less common and is associated with URI or allergic rhinitis. Symptoms range from mild discomfort equilibrating pressure in the ears to actual barotrauma. The majority of patients experiencing these symptoms experience relief after the administration of nasal decongestants or nasal steroids and can complete the hyperbaric therapy. To mitigate against this known risk, patients receive detailed instruction in the proper methods for equilibrating the pressure in the ears and sinuses prior to hyperbaric therapy.

**Claustrophobia** appears to be present in about 2% of the general patient population, and may be higher even in the multiplace and mono-place chamber. True claustrophobia causes people to sweat and experience tachycardia in elevators, CT scanners and MRI machines. Study participants with true claustrophobia will be excluded from the study. It is far more common for people to experience confinement anxiety, rather than true claustrophobia. The majority of patients experiencing confinement anxiety are able to complete hyperbaric therapy sessions without difficulty. Study participants who are unable to overcome the symptoms of confinement anxiety will be allowed to complete the study and occasionally, sedation will be used if the participant has people available to drive them to and from the DGMC.

**Vision changes**, typically a progressive myopia, can occur in some patients undergoing prolonged treatment courses of HBOT. The exact mechanism is unclear, but is apparently lenticular in origin. The incidence documented in the literature ranges from 20% to as high as 69%, with complete reversal of the refractive changes occurring in nearly all patients except those with pre-existing cataracts. Refractive changes developed in 24 of 25 patients studied in Sweden, undergoing prolonged courses of HBOT of 150-850 daily exposures. With one possible documented exception, new cataracts do not develop within clinical courses of 20-50 sessions.

**Pulmonary barotraumas** with or without air embolism may rarely occur during decompression, necessitating careful analysis of risk versus benefit. The actual risk is indeterminate, but is known to be higher in patients with asthma or pulmonary blebs. To protect against these risks, the DGMC hyperbaric chamber does not permit wheezing asthmatic patients to enter the hyperbaric chamber. This risk is minimal for controlled asthmatics that are compliant with their medication. Similarly, a chest x-ray and pulmonary consultation will be required of any patient with known pulmonary disease who wishes to enroll in the study. Any participants with known pulmonary disease who wish to enroll in the study will be permitted to do so if they are cleared by their pulmonologist.

**Cardiovascular responses and flash pulmonary edema** are rare complications of unknown risk and unknown incidence due to the rate-dependent reduction in cardiac output with an increase in peripheral vascular resistance that hyperbaric oxygen induces. These effects are well tolerated by normal individuals, but patients with decreased left ventricular ejection fraction must be monitored for the rare complication of acute pulmonary edema. In as little as ten minutes, these changes in cardiac output can lead to a collection of fluid in the lungs known as flash pulmonary edema. The incidence is unknown. The current inability to accurately identify patients susceptible to this rare complication requires careful evaluation of known heart failure patients prior to hyperbaric therapy. Potential study participants with known heart failure will be required to have an echocardiogram and a cardiology consultation prior to enrolling in the study. Study participants with heart failure will be allowed to enroll in this study if they are cleared by their cardiologist.

**Oxygen associated risks include central nervous system toxicity** manifest by focal and or generalized seizures. Recent surveys that include a total of 138,968 patient therapies at three different facilities indicate a combined incidence of ~ 0.03% for three 30-minute oxygen breathing periods at 2.4 to 2.5 atm abs. Earlier estimates of the seizure rate during HBO exposures at 2.0 to 3.0 atm abs reported a convulsion incidence of 0.01%. HBO2-induced seizures only occur during the exposure to high levels of O2 in the hyperbaric chamber at pressure, and there are no residual effects. However, if not diagnosed and managed, seizures can recur on re-exposure to HBO2.

**Hypoglycemia:** In diabetic patients taking hypoglycemic medications, there is a risk of hypoglycemia and associated effects. To protect against this complication, the DGMC hyperbaric policy requires blood sugar levels of at least 120 in diabetic patients prior to

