**4. Purpose of Investigation**

This is a pilot study. The purpose of this investigation is to determine the effects and feasibility of using hyperbaric oxygen therapy (HBO2) for the treatment of rheumatoid arthritis joint pain and prevention of disease progression. In this study it is our intention to not only evaluate effects and feasibility but time, cost, adverse events and effect size in an attempt to predict an appropriate sample size and improve on the study design prior to a more extensive study.

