**Risk to Benefit Ratio:**

Risks are well understood, treatable and with few exceptions of low magnitude. The potential benefits such as reduction in pain, improved sleep, decreased RA disease activity are extremely beneficial. As such, potential direct benefits to the subjects and to future treatments outweigh the risks that, as mentioned above, are rare and minor in the well-selected patient.

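### Section 6.5 calls the risks rare while printing 20–69% for vision change, and no scheduled instrument asks about vision

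*Combined protocol and SAP*

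**What the plan says.** The first risk described under Risks/ Inconveniences (Section 6.5) is middle ear barotrauma and eustachian tube dysfunction, which "is the most common side effect of HBOT with an incidence of at least 2" per cent. No upper figure is given, and the text does not say whether the rate is per patient or per session.

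Two paragraphs later, vision changes, typically progressive myopia, "can occur in some patients undergoing prolonged treatment courses of HBOT". For these, "The incidence documented in the literature ranges from 20% to as high as 69" per cent, with "complete reversal of the refractive changes occurring in nearly all patients except those with pre-existing cataracts". A separate sentence reports a long-course study: "Refractive changes developed in 24 of 25 patients studied in Sweden, undergoing prolonged courses of HBOT of 150-850 daily exposures". The paragraph ends with a statement about new cataracts in courses of 20–50 sessions.

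The Risk to Benefit Ratio paragraph, later in Section 6.5, concludes that the potential benefits "outweigh the risks that, as mentioned above, are rare and minor in the well-selected patient". Its opening sentence also allows for a few exceptions to low magnitude.

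Section 4 lists "time, cost, adverse events and effect size" among the things the pilot is to evaluate, to help plan a larger study. Section 6.4 plans 30 sessions. Section 6.6 allows up to 20 subjects, with recruitment continuing until there are 10 complete data sets.

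**The concern.** The closing risk statement refers back to the risks just described, and one of them carries a printed incidence of 20–69%. A reader weighing risk against benefit is told that the risks are rare by the same section that reports one affecting between a fifth and two thirds of patients. Ear barotrauma is ranked first on a figure that, as printed, is far lower.

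The second issue is measurement. Section 6.7 treats Section 6.5 as the list of potential adverse events, so vision change is an anticipated event. The Study Visits table in Section 6.4 schedules DAS28, RAPID 3, PSQ-3 and VAS pain, which address disease activity, function, pain and sleep. None is described as covering vision. At stake are the accuracy of the risk statement and the quality of the adverse event rate that the pilot passes to the next study.

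**Working it through.** The incidences are literature figures with no calculation behind them, so there is nothing to reproduce. The check compares the statements and works out what they imply.

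**1. Is *rare* compatible with 20–69%?**
- Read per patient, 20–69% is not rare.
- Read per session, the proportion of patients affected over a course could not be lower than the per-session rate, so it is still not rare.
- The restriction to well-selected patients does not help. No inclusion or exclusion criterion in Section 6.6 selects on vision. Pre-existing cataract, the one group excepted from near-complete reversal, is not mentioned there. This is an observation about the wording, not a proposal on eligibility.

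**2. Is *most common* contradicted?** The 2% is a lower bound without a denominator.
- Per patient and close to the floor, it lies below 20–69%.
- Per session, assuming independent sessions, 30 sessions give 1 − (1 − 0.02)^30 = 1 − 0.98^30 = 0.455, or about 45% of patients. That lies inside 20–69%, so the ranking could hold, but *rare* would then fail for ear barotrauma too.

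The section does not use a single clear denominator: its seizure incidence is counted over patient therapies.

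**3. Does 20–69% apply to 30 sessions?** The vision paragraph ties the effect to prolonged courses and does not define the term for this range. The study of 150–850 exposures gives 24/25 = 96%, which is outside the range, so the range is not simply that study's result. The 20–50 session sentence concerns new cataracts and does not settle the question for myopia. The point stays open.

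**4. Implied counts if the range does apply** (assumption; expected cases = n × p, chance of at least one = 1 − (1 − p)^n):

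| n | p | Expected cases | Chance of at least one |
|---|---|---|---|
| 10 | 0.20 | 2.0 | 1 − 0.80^10 = 89% |
| 10 | 0.69 | 6.9 | 1 − 0.31^10 > 99.9% |
| 20 | 0.20 | 4.0 | 1 − 0.80^20 = 98.8% (0.9885) |
| 20 | 0.69 | 13.8 | 1 − 0.31^20 > 99.9% |

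**5. Where would vision change be recorded?** Sections 6.4 and 6.7 provide daily monitoring by hyperbaric physicians during treatment, real-time follow-up for adverse events, and weekly cumulative review. The Incidental Findings paragraph adds an abbreviated history and examination at later rheumatology visits. None specifies a question on vision. After the last session, the remaining scheduled visits are the rheumatology visits at months 3 and 6, so reversal is not systematically checked.

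**The case against.** The case on the other side is that this is loose wording and nothing is hidden. The incidence range, the long-course study, the reversibility and the cataract exception are all printed. *Minor* has real support, since the change reverses in nearly all patients. The closing sentence is qualified, and existing surveillance is close during treatment. All of this stands, and it limits the point to the word *rare*, the missing denominators and course lengths, and the absence of a solicited question. The allowance for exceptions concerns magnitude, not frequency, so it does not rescue *rare*.

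A reader might infer three stronger conclusions that the documents do not support:

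- **That the figures disprove the ranking of ear barotrauma, or that vision change is many times as frequent.** A ratio to 2% treats a floor as a point estimate and assumes a shared per-patient denominator. Neither is stated, so no ratio should be quoted.
- **That vision change will be the pilot's most frequent event.** This assumes that 30 sessions count as a prolonged course, which the text does not say.
- **That the adverse event rate will be falsely low.** Daily contact may well catch spontaneous complaints, and no adverse event form is among the documents, so a missing question is inferred from silence. Under-reporting is possible but not shown.

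**Conclusion.** The point holds in a limited form. *Rare* in the Risk to Benefit Ratio paragraph is inconsistent with the 20–69% printed earlier in the same section, whichever denominator is intended. *Most common* for ear barotrauma is unsupported by the printed figures but not refuted.

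The size is conditional. If 20–69% applies to a 30-session course, about 2 to 7 of 10 completers or 4 to 14 of 20 subjects would have a vision change, mostly reversible. If the range belongs to longer courses, the conflict weakens, but the protocol would need to say so.

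Because adverse events are a stated purpose of the pilot, a systematic count of this anticipated event is worth having. Sample size, power and the efficacy outcomes are not affected.

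**What to change.** 1. Under Risks/ Inconveniences, give each incidence its denominator (per patient or per session) and the course length it refers to, and state whether the 20–69% range is thought to apply to 30 sessions. Keep *most common* for ear barotrauma only if the completed figures support it.
2. In the Risk to Benefit Ratio paragraph, replace *rare* with wording that fits those figures, for example that vision change may be frequent but usually reverses, except with pre-existing cataracts. Check that the consent form agrees. It was not available for this review, so no error is claimed there.
3. Add one solicited yes/no question on changed distance vision since the start of treatment. Ask it when questionnaires are already given during HBO2, at the completion contact (where labs are already drawn), and at months 3 and 6. Tabulate the answers as an adverse event, with the number asked as denominator. The month 3 and 6 answers also give a check of reversal.

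The cost is a wording amendment and one extra question at existing contacts, with no added visit or eye examination. The downside is a possibly higher reported adverse event rate. The gain is a systematic rate and a check of reversal.

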**For Protocol Office use only:**

Protocol title: The Effects of Hyperbaric Oxygen on  
Rheumatoid Arthritis: a Pilot Study.  
FDG20160004H wAMD13

investigator name redacted 28 Jan 20

DGMC Human Research Protocol Template

receiving hyperbaric therapy. Diabetics with blood sugar below this level receive juice and crackers, and may have blood glucose rechecked prior to therapy. Hyperbaric staff are always present in the hyperbaric chamber, and can monitor for signs or symptoms of hypoglycemia. At least one member of the hyperbaric team is present in the chamber for each eight patients in the chamber. If symptoms occur, staff will recheck the blood glucose immediately, and administer juice and crackers if needed. Following the completion of hyperbaric therapy, diabetic patients are again tested for blood sugar level. Patients must have a blood sugar level of at least 100 prior to leaving the hyperbaric medicine department, or be cleared by the hyperbaric physician.

**Fire** is always a risk with pressurized oxygen in high concentrations. Hyperbaric chamber patients are not allowed to smoke or carry lighters or flammable materials in the hyperbaric chamber. Until a recent explosion in a non-certified chamber, there had not been a fire in a United States hyperbaric chamber since 1968.

There is an **inconvenience of the time** associated with the study. There are approximately 40 appointments over a six month period. Thirty of them are two hour appointments for hyperbaric treatments.

**Blood draws:** there is a risk associated with blood draws. The risks of taking blood include: Pain, bruise at the point where the blood is taken, redness and swelling of the vein, infection and a rare risk of fainting.

**Ultrasound:** There is no risk associated with ultrasound.

**MRI:** We will be doing a MRI with and without contrast looking at the wrist from the distal radius to the mid diaphysis of the proximal phalanges. Risks include allergy to MRI contrast which is extremely rare. There is a risk of nephrogenic systemic fibrosis with poor renal function (GFR<30) that is screened for (see Attach 11) if the subject is over 50 years of age or has a history of renal insufficiency.

**Benefits:**

The purpose of this study is to determine the effectiveness of HBOT on rheumatoid arthritis. The use of HBO2 in patients with RA may or may not include decreased joint pain, increased activity level, improvement in sleeping patterns. Depending on study outcomes it may benefit society, possibly diminished need for use of immunosuppressive rheumatologic medications.

**Risk to Benefit Ratio:**

Risks are well understood, treatable and with few exceptions of low magnitude. The potential benefits such as reduction in pain, improved sleep, decreased RA disease activity are extremely beneficial. As such, potential direct benefits to the subjects and to future treatments outweigh the risks that, as mentioned above, are rare and minor in the well-selected patient.

**6.6. Subject Population**

**Age Range:**   $\geq 18$  y/o  Children ( $\leq 18$ )

**Sex:**  Male  Female

**Vulnerable Population:**  No  Yes (explain)

**Number of Subjects:**

- Total Number of Subjects: 20
- Number of Subjects Planned for DGMC: 20

A total of up to 20 subjects will be recruited. We will continue to recruit and treat until 10 complete data sets have been obtained. In the event that ten total data sets are obtained and additional subjects are in the process of the intervention, at the PI's discretion, those additional subjects will receive full treatment.

